21.1. Definitions and Classification

Adverse event definitions are provided in Table 21.1-1. Administrative edits were made to combine definitions from ISO 14155-2011 and MEDDEV 2.7/3 12/2010.

Table 21.1-1: Adverse Event Definitions

Term	Definition
Adverse Device Effect (ADE)	Adverse event related to the use of an investigational medical device NOTE 1: This definition includes any adverse event resulting from

Table 21.1-1: Adverse Event Definitions

Term	Definition

Ref: ISO 14155-2011
 
Ref: MEDDEV 2.7/3 12/2010
	
insufficient or inadequate instructions for use, the deployment, the implantation, the installation, the operation, or any malfunction of the investigational medical device.
 
NOTE 2: This definition includes any event resulting from use error or from intentional misuse of the investigational medical device.

Serious Adverse Event (SAE)
 
Ref: ISO 14155:2011
	
Adverse event that:
 
Led to a death
 
Led to serious deterioration in the health of the subject, that either resulted in:
 
 ○ a life-threatening illness or injury, or ○ a permanent impairment of a body structure or a body function, or ○ in-patient or prolonged hospitalization, or ○ medical or surgical intervention to prevent life-threatening illness or injury or permanent impairment to a body structure or a body function, ○ Led to foetal distress, foetal death or a congenital abnormality or birth defect 
Note: For the purpose of this study, only events that led to death will be reported as SAE.

Serious Adverse Device Effect (SADE)
 
Ref: ISO 14155-2011
 
Ref: MEDDEV 2.7/3 12/2010
	
Adverse device effect that has resulted in any of the consequences characteristic of a serious adverse event.

Unanticipated Serious Adverse Device Effect (USADE)
 
Ref: ISO 14155-2011
 
Ref: MEDDEV 2.7/3 12/2010
	
Serious adverse device effect which by its nature, incidence, severity, or outcome has not been identified in the current version of the risk analysis report.
 
NOTE 1: Anticipated serious adverse device effect (ASADE) is an effect which by its nature, incidence, severity or outcome has been identified in the risk analysis report.

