21.3. Investigator Reporting Requirements

Event reporting on RESPOND study is limited to SAE that lead to death, ADE, SADE, USADE, device deficiencies and VARC events regardless of seriousness and device relationship. The communication requirements for reporting to BSC are as shown in Table 21.3-1.

Table 21.3-1: Investigator Reporting Requirements

Event Classification	Communication Method	Communication Timeline
Unanticipated Serious Adverse Device Effect (USADE)	Complete AE eCRF page with all available new and updated information	
 Within 1 business day of first becoming aware of the event¹. Terminating at the end of the study
Serious Adverse Event (SAE) that led to death, Serious Adverse Device Effects (SADE), and serious VARC events	Complete AE eCRF page with all available new and updated information	
 Within 2 business days of first becoming aware of the event¹ or as per local/regional regulations. Reporting required through the end of the study
	Provide relevant source documentation (unidentified) for reported event	
 When documentation is available
Adverse Device Effects and non-serious VARC events	Complete AE eCRF page with all available new and updated information	
 As soon as possible after becoming aware of the information¹ Reporting required through the end of the study
Device Deficiencies (including but not limited to failures,	Complete applicable CRF fields/forms with all available new and updated	
 Within 1 business day of first becoming aware of the event¹

Table 21.3-1: Investigator Reporting Requirements

Event Classification	Communication Method	Communication Timeline
malfunctions, and product nonconformities) Note: Any Device Deficiency that might have led to a serious adverse device effect if a) suitable action had not been taken or b) intervention had not been made or c) if circumstances had been less fortunate is considered a reportable event.	information.	and as per local/regional regulations • Reporting required through the end of the study

¹ The “become aware date” for an event that requires reporting per the protocol is the date that study personnel listed on the Delegation of Authority Log identify or are notified of the event. Personnel may become aware via any of the following (inclusive but not limited to):

- Patient or patient’s caregiver

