RIGHT VENTRICULAR INSUFFICIENCY	
 • Defined as sequelae of right ventricular failure including the following. 
 ○ Significantly decreased right ventricular systolic and/or diastolic function ○ Tricuspid valvular regurgitation secondary to elevated pressure • Clinical symptoms to include the following. 
 ○ Hepatic congestion ○ Ascites ○ Anasarca ○ Presence of “hepato-jugular reflux” ○ Edema 
Severe right ventricular dysfunction or severe pulmonary hypertension is primary or secondary pulmonary hypertension with PA systolic pressures greater than 2/3 of systemic pressure.

SERIOUS ADVERSE EVENT (SAE)	Adverse event that led to a death
SERIOUS ADVERSE DEVICE EFFECT (SADE)	Adverse device effect that has resulted in any of the consequences characteristic of a serious adverse event
SOURCE DATA (per ISO 14155:2011)	All information in original records of clinical findings, observations, or other activities in a clinical investigation, necessary for the reconstruction and evaluation of the clinical investigation
SOURCE DOCUMENT (per ISO 14155:2011)	Printed, optical or electronic document containing source data. Examples: Hospital records, laboratory notes, device accountability records, photographic negatives, radiographs, records kept at the investigation center, at the laboratories and at the medico-technical departments involved in the clinical investigation.

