TRANSIENT ISCHEMIC ATTACK (TIA)	
 • Transient episode of focal neurological dysfunction caused by brain, spinal cord, or retinal ischemia, without acute infarction • Duration of a focal or global neurological deficit is <24 h • Neuroimaging does not demonstrate a new hemorrhage or infarct (if performed) 
Note: The difference between TIA and ischemic stroke is the presence of tissue damage or new sensory-motor deficit persisting >24 hours. By definition, TIA does not produce lasting disability.

UNANTICIPATED SERIOUS ADVERSE DEVICE EFFECT (USADE)	
Serious adverse device effect which by its nature, incidence, severity, or outcome has not been identified in the current version of the risk analysis report
 
Note: An anticipated serious adverse device effect (ASADE) is an effect which by its nature, incidence, severity, or outcome has been identified in the risk analysis report.

UNPLANNED USE OF CPB	
Unplanned use of cardiopulmonary bypass (CPB) for hemodynamic support at any time during the TAVR procedure

VALVE EMBOLIZATION	
The valve prosthesis moves during or after deployment such that it loses contact with the aortic annulus.

VALVE	
Includes valve migration, valve embolization, ectopic valve deployment, or

Table 26.2-1: Definitions

Term	Definition
MALAPPOSITION	transcatheter aortic valve (TAV)-in-TAV deployment.
VALVE MIGRATION	After initial correct positioning the valve prosthesis moves upward or downward within the aortic annulus from its initial position, with or without consequences (e.g., regurgitation).
VALVE-RELATED DYSFUNCTION	Mean aortic valve gradient ≥ 20 mmHg, EOA ≤ 0.9 - 1.1 cm ² , and/or DVI < 0.35 AND/OR moderate or severe prosthetic valve aortic regurgitation (per VARC definition)

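### Tables 21.1-1 and 26.2-1 define a serious adverse event differently; applied literally, the fatal-only version could move non-fatal serious device effects out of SADE/USADE and away from their fixed reporting deadlines

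*Combined protocol and SAP*

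**What the plan says.** Section 21.1 opens with "Adverse event definitions are provided in Table 21.1-1". In that table an SAE is an event that caused death, or one of a set of non-fatal outcomes introduced by "Led to serious deterioration in the health of the subject, that either resulted in": life-threatening illness, permanent impairment, hospital stay, or an intervention to prevent these. A note under the entry adds "For the purpose of this study, only events that led to death will be reported as SAE".

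Section 26.2 also presents itself as the place where the protocol's terms are defined. The SAE entry in Table 26.2-1 reads in full "Adverse event that led to a death". The next entry defines a SADE as "Adverse device effect that has resulted in any of the consequences characteristic of a serious adverse event". A USADE is defined in the same table as a kind of SADE: "Serious adverse device effect which by its nature, incidence, severity, or outcome has not been identified" in the current risk analysis report.

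Table 21.3-1 in Section 21.3 sets the investigator's deadline by event class:

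- USADE: 1 business day.
- Fatal SAE, SADE and serious VARC events: 2 business days, or as local or regional rules require.
- ADE and non-serious VARC events: "As soon as possible after becoming aware of the information", with no day limit.
- Device deficiencies: 1 business day.

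**The concern.** The note in Table 21.1-1 limits which events are entered under the SAE label. It leaves the list of serious consequences intact, so a SADE or USADE can still be non-fatal. Table 26.2-1 turns that reporting limit into the definition. Once death is the only consequence of an SAE, the SADE and USADE entries beneath it cover fatal device effects only.

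The same event can therefore carry two classifications depending on which table a site opens. What is at stake is the deadline for telling the sponsor about non-fatal serious device effects, including unanticipated ones, and the consistency of SADE and USADE counts across up to 60 centers and 5 years of follow-up. The synopsis lists SADE, USADE and ADE among the safety parameters, so the split between them is a reported output of the study.

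**Working it through.** No arithmetic applies and the plan states no figure to reproduce. The check is to follow one event through each table's definitions and then through Table 21.3-1.

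**Step 1: the chain of definitions.** USADE depends on SADE, and SADE depends on the consequences of an SAE. The SADE and USADE wording is essentially the same in both tables, so any difference in scope comes from the SAE entry alone.

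**Step 2: classification and deadline under each table.**

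| Device-related event | Using Table 21.1-1 | Using Table 26.2-1 literally |
|---|---|---|
| Fatal, anticipated | SADE, 2 business days | SADE, 2 business days |
| Fatal, unanticipated | USADE, 1 business day | USADE, 1 business day |
| Non-fatal serious, anticipated, not a VARC event | SADE, 2 business days | ADE, no day limit |
| Non-fatal serious, unanticipated, not a VARC event | USADE, 1 business day | ADE, no day limit |
| Non-fatal serious, also a VARC event | SADE or USADE, 2 or 1 business days | ADE; 2 business days if handled as a serious VARC event, otherwise no day limit |

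The two readings agree on fatal events and part on every non-fatal one.

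**Step 3: does the VARC route close the gap?** Only partly. First, the protocol gives no separate meaning of serious for VARC events; its only seriousness criteria are the two SAE entries. If serious is also read from Table 26.2-1, a non-fatal VARC event is non-serious and has no day limit. Second, some device effects are outside the VARC list in Section 7.3. Hemolysis, for example, is defined in Table 26.2-1 but is not among the listed events; if it were device-related, serious and non-fatal, it would have no VARC route. Third, an unanticipated event that does take the serious-VARC route moves from 1 business day to 2.

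**Step 4: does the device-deficiency route close it?** No. Section 21.4 says deficiencies are not themselves reported as events and that a resulting event is recorded separately, so the event still has to be classified. The ADE definition also covers events arising from deployment or implantation, which need not involve a deficiency.

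**Step 5: is the event lost?** No. Section 21.3 keeps all ADEs and VARC events reportable, and Section 18 calls for source verification of subjects with an ADE as well as those with a SADE or USADE.

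**The case against.** The strongest reply is that the protocol's operative text already favors the broad meaning. Section 21 governs reporting and names Table 21.1-1 as its source, at the start of Section 21.1 and again after that table. Section 8, Section 21.3 and the synopsis list fatal SAEs separately from SADE and USADE. If every SAE were fatal, the qualifier would be redundant, and a separate SADE class would add nothing to the 2-business-day row. The SADE wording speaks of consequences in the plural, which sits badly with a list of one. Much of the serious harm to be expected with this device is on the VARC list and is collected whatever its relation to the device. Section 12 plans no SADE or USADE analysis, so no endpoint, test or threshold moves.

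All of that stands, and it makes Table 21.1-1 the better reading. It rules out the stronger conclusion a reader might draw, that non-fatal serious device effects do drop out of expedited reporting. That happens only where a site uses the glossary in place of the safety section.

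A reader might also try to size the problem from the 10% expected 30-day mortality or from the major stroke in REPRISE I. Neither works. The first is a per-subject death rate and says nothing about the fatal share of serious device effects. The second is a VARC event with its own reporting route, and the protocol does not say that it was device-related.

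The reply does not remove the conflict. Section 26.2 also claims to define the terms, no clause gives either table precedence, and the note in Table 21.1-1 can be misread in exactly the way Table 26.2-1 is written. The serious-VARC safeguard rests on the same disputed word.

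**Conclusion.** This is an internal inconsistency, wrong as written, and should be corrected. Tables 21.1-1 and 26.2-1 give incompatible definitions of an SAE, and through it of SADE and USADE. If Table 26.2-1 is applied literally, a non-fatal serious device effect could be classed as an ADE, go from a 1- or 2-business-day deadline to none, and be left out of the SADE/USADE counts. The exposure is smaller for events reported as serious VARC events, which keep a 2-business-day limit. Where local or regional rules set their own deadline, that may also limit the delay.

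The conclusion assumes only that some sites will consult the glossary. The documents give no basis for estimating how many sites or events that would involve, so the effect is stated as a change of reporting route and not as a rate. The decision to collect only fatal events under the SAE label is deliberate and is not in question. The mortality and regurgitation tests are unaffected.

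**What to change.** Reconcile the two tables. Align the SAE entry in Table 26.2-1 with the consequence list in Table 21.1-1. Beside both entries, state that the fatal-only limit decides which events are collected under the SAE label, and that it does not alter the seriousness criteria used for SADE, USADE and serious VARC events. The last of these matters because the protocol gives VARC events no seriousness criteria of their own.

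The cost is one table entry and one clarifying sentence in an amendment, with ethics committee approval if Section 14 requires it, plus a short note to sites. The new text comes from the protocol's own safety section.

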	
Valve System if repositioning is attempted
 
 ○ Successful retrieval (complete resheathing of the Lotus Valve in the catheter and removal from the body) of the Lotus Valve System if retrieval is attempted ○ Grade of paravalvular aortic valve regurgitation 
 ● Physicians Preference Test (PPT), including device deficiencies, to measure device usability and ease of use peri-procedurally. ● Prosthetic aortic valve performance as measured by transthoracic echocardiography (TTE) and assessed by an independent core laboratory, including effective orifice area, mean and peak aortic gradients, peak aortic velocity, and grade of aortic regurgitation, pre-discharge and at 1 year. Site reported TTE measures will be collected at 30 days and annually from 2 through 5 year follow up per local standard of care for TAVI. ● Health status as evaluated by EuroQoL (EQ-5D) Quality of Life questionnaire at baseline, 30 days, 1, 3 and 5 year follow up, during in-person clinic visit or via postal mail. ● New York Heart Association (NYHA) functional classification at baseline, discharge, 30 days, 1 year and annually through 5 year follow up. 
^aKappetein AP, et al. J Am Coll Cardiol. 2012;60:1438-1454 ^bLeon M, et al. J Am Coll Cardiol. 2011;57:253-269
 
NOTE: Additional measurements will be assessed in the additional cohort of 80 patients through 30 day follow up.

Safety Parameters	
 ● Any serious adverse event (SAE) that led to death, serious adverse device effect (SADE), adverse device effect (ADE), unanticipated serious adverse device effect (USADE), and VARC event regardless of seriousness and device relationship will be collected through complete subject follow up. ● All-cause mortality and stroke events will be adjudicated by an independent Clinical Events Committee (CEC) through complete subject follow up. ● Reporting of device deficiencies will follow applicable regional post-market safety surveillance requirements.
Follow-up Schedule	
For the main cohort of 1000 subjects, follow up will occur at 30 days and 1, 2, 3, 4 and 5 years post index valve implantation for all enrolled subjects. Follow-up visit at 1 year post valve implantation

RESPOND: Repositionable Lotus Valve System – Post Market Evaluation of Real World Clinical Outcomes	

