7.2. Secondary Endpoints

The following secondary endpoints will be measured according to current VARC guidelines:

- Safety composite of all-cause mortality and disabling stroke at 30 days and 1 year
- In-hospital mortality
- The VARC efficacy composite at 1 year, including all-cause mortality; all stroke (disabling and non-disabling); re-hospitalization for valve-related symptoms or worsening congestive heart failure (NYHA class III or IV); and prosthetic valve-related dysfunction (mean aortic valve gradient ≥ 20 mmHg, effective orifice area (EOA) ≤ 0.9 – 1.1 cm² and/or Doppler velocity index (DVI) < 0.35 m/s, AND/OR moderate or severe prosthetic valve aortic regurgitation)
- Time related valve safety composite at 1 year, including structural valve deterioration (valve-related dysfunction requiring repeat procedure [TAVI or SAVR]); prosthetic valve endocarditis; prosthetic valve thrombosis; thromboembolic events (e.g. stroke) and VARC bleeding, unless clearly unrelated to valve therapy based on investigator assessment (e.g. trauma)
- Clinical endpoints at 30 days defined according to current VARC guidelines:
 - Life-threatening bleeding
 - Acute kidney injury—Stage 2 or 3 (including renal replacement therapy)
 - Coronary artery obstruction requiring intervention
 - Major vascular complication
 - Valve-related dysfunction requiring repeat procedure (BAV, TAVI, or SAVR)
 - New conduction disturbances (LBBB, AVB, RBBB) and need for permanent pacemaker implantation

- Grade of paravalvular aortic valve regurgitation pre-discharge as measured by transthoracic echocardiography (TTE) and assessed by an independent core laboratory. The moderate and severe paravalvular aortic regurgitation rate will be compared to a pre-specified performance goal.

NOTE: Secondary endpoints will be assessed in the additional cohort of 80 patients through 30 day follow up.

7.3. *Additional Measurements*

Additional measurements will be collected as specified below:

- The following events will be collected based on the current VARC definitions^{44,45}:
 - All-cause death (cardiovascular and non-cardiovascular)
 - Stroke: disabling and non-disabling
 - Myocardial infarction (MI): periprocedural (≤ 72 hours post index procedure) and spontaneous (> 72 hours post index procedure)
 - Bleeding: life-threatening (or disabling), major and minor

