11.7. Follow-up

All implanted subjects enrolled in the main cohort of 1000 subjects will be evaluated at 30 days, 1, 2, 3, 4 and 5 years post index procedure. Follow-up visit at 1 year post valve implantation should be conducted via outpatient clinic visit. Follow-up visits at 30 days and 2 through 5 years may be conducted in person (preferred) and via telephone interview. Subjects with no Lotus Valve implanted will be followed for safety through 30 days after the initial attempted index procedure.

The additional cohort of approximately 80 subjects will be contacted for follow up at 30 days post valve implantation.

It is important that the follow-up visit schedule be maintained as closely as possible for all subjects. Boston Scientific recognizes that subjects may not be able to return for all scheduled visits at precisely the date required, and therefore, a period of time in which each visit should be conducted is indicated in Table 11.1-1. Each follow-up visit must be performed by trained study personnel. Data from collected tests and images as well as medical assessments will be recorded in source documentation and captured in the eCRFs.

In the event that study personnel learn of a subject's hospitalization outside the study center, the center should make every effort to obtain copies of reports or results based on tests (e.g., echocardiogram) and/or procedures performed on the study subject.

11.7.1. 30-Day Follow-up (30±7 days)

All enrolled subjects must be evaluated 30 days after the index procedure. The 30-day follow-up visit may be conducted in person (preferred) or via telephone interview. During the 30-day follow-up, the following assessments are to be collected:

- Complete safety event assessment, including any SAE that led to death, ADE, SADE, USADE, device deficiencies with associated treatment, and any VARC events regardless of seriousness and device relationship.
- All antiplatelet and other cardiovascular medications administered in accordance with society guidelines⁴³ and local standard of care. Subjects should be treated with aspirin and clopidogrel for at least 1 month following valve implantation. Subsequent antiplatelet therapy should be at the investigator's discretion, or in accordance with country-specific labeling for the medications. If oral anti-coagulation is indicated after valve implantation, antiplatelet therapy should consist of either aspirin or thienopyridine. Combination

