11.9. Study Completion

All implanted subjects enrolled in the main cohort of 1000 subjects will be followed for the duration of 5 years post index procedure. A subject's participation in the study will conclude after completion of the 5 year follow-up visit.

For subjects enrolled in the additional 80-subject cohort, participation in the study will conclude after completion of the 30-day follow-up visit.

12. Statistical Considerations

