12.1.3. Statistical Methods

All subjects who are enrolled will be eligible for evaluation. Handling of dropouts and missing data will depend on their frequency and the nature of the outcome measure. The distribution of prognostic factors between subjects with and without data will be examined. Methods to eliminate or minimize bias will be implemented and described completely. Statistical models that account for censored data will be employed in appropriate circumstances (e.g., for time-to-event outcomes). Sensitivity analyses, including a tipping-point analysis for the primary endpoint, will be conducted to assess the impact of different assumptions on interpretation of the results. Outlier values will be evaluated for their validity. Suspected invalid data will be queried and corrected in the database prior to statistical analysis.

The data of the additional cohort of approximately 80 subjects will be summarized using descriptive statistics and will not be pooled with the first cohort of 1,000 subjects in the data analysis. No statistical hypotheses will be tested in the additional cohort.

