	
results in death
 
 • No other readily identifiable nonstroke cause for the clinical presentation (e.g., brain tumor, trauma, infection, hypoglycemia, peripheral lesion, pharmacological influences), to be determined by or in conjunction with designated neurologist • Confirmation of the diagnosis by at least one of the following. 
 ○ Neurology or neurosurgical specialist ○ Neuroimaging procedure (MRI or CT scan), but stroke may be diagnosed on clinical grounds alone 
Note 3: Subjects with non-focal global encephalopathy will not be reported as a stroke without unequivocal evidence based upon neuroimaging studies (CT scan or brain MRI).
 
Stroke Definitions
 
Diagnosis as above, preferably with positive neuroimaging study
 
 • Non-disabling: Modified Rankin Scale (mRS) score <2 at 90 days OR one that does not result in an increase of at least one mRS category from an individual's pre-stroke baseline • Disabling: Modified Rankin Scale score ≥2 at 90 days AND an increase of at least one mRS category from an individual's pre-stroke baseline 
Note 4: Modified Rankin Scale assessments should be made by qualified individuals according to a certification process.
 
Note 5: Assessment of the mRS score should occur at all scheduled visits in a study; mRS also should be performed after a stroke and at 90 days after the onset of any stroke.

STRUCTURAL VALVE DETERIORATION	
Component of time-related valve safety defined as follows.
 
 • Valve-related dysfunction: Mean aortic valve gradient ≥20 mmHg, EOA ≤0.9-1.1 cm², and/or DVI <0.35 AND/OR moderate or severe prosthetic valve regurgitation (per VARC definition) • Requiring repeat procedure (TAVR or SAVR).
TAV-IN-TAV DEPLOYMENT	
An additional valve prosthesis is implanted within a previously implanted prosthesis because of suboptimal device position and/or function during or after the index procedure.

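### In the additional cohort no stroke can be confirmed as disabling, because the definition needs a 90-day mRS and participation ends at the 30-day visit

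*Combined protocol and SAP*

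**What the plan says.** All references are to the combined protocol and SAP.

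- **Definition.** Section 26.2, Table 26.2-1 (Stroke): "Disabling: Modified Rankin Scale score ≥2 at 90 days AND an increase of at least one mRS category", relative to the individual's pre-stroke baseline. A stroke is non-disabling if the mRS is below 2 at 90 days, or if it does not raise the mRS by at least one category; that second branch states no time. Note 5 asks for an mRS at all scheduled visits, after a stroke, and 90 days after the onset of any stroke, with no exception by cohort.
- **Endpoint.** Section 7.2 lists "Safety composite of all-cause mortality and disabling stroke at 30 days and 1 year" and adds: "Secondary endpoints will be assessed in the additional cohort of 80 patients through 30 day follow up". The synopsis says the same of the additional measurements ("Additional measurements will be assessed in the additional cohort of 80 patients through 30 day follow up"), and these include the split of strokes into disabling and non-disabling.
- **Follow-up.** Section 11.9: "For subjects enrolled in the additional 80-subject cohort, participation in the study will conclude after completion of the 30-day follow-up visit". Section 11.7.1 gives that visit a window of 7 days either side. Section 8 and footnote 9 of Table 11.1-1 collect safety events in this cohort through 30 days only.
- **Handling.** Section 12.1.3: "Handling of dropouts and missing data will depend on their frequency and the nature of the outcome measure". It says nothing specific about a stroke that has no 90-day score. It also says that this cohort is summarised descriptively, is not pooled with the main cohort, and has no hypothesis tested.

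**The concern.** One component of the composite depends on a measurement that falls due after every subject in the cohort has left. This is not sporadic dropout. The score is out of reach by design for each non-fatal stroke, so general missing-data wording does not settle what to do.

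The reported figure then depends on a choice that the supplied documents do not make. If only strokes that meet the disabling definition within participation count, none can, and the composite equals all-cause mortality, which Section 7.1 already makes this cohort's primary endpoint. If every unconfirmed stroke counts, the composite becomes death or any stroke. In a safety composite, that choice should not be made after the strokes have been seen.

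**Working it through.** The plan states no figure to reproduce here: the additional cohort has no alpha, power or margin. The check is date arithmetic, followed by the size of the effect.

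**1. Can the 90-day score fall within participation?**

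Inputs: visit window day 23 to day 37 (30 ± 7, Section 11.7.1); score due 90 days after stroke onset (Table 26.2-1, Note 5); participation ends at the visit (Section 11.9).

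Gap from visit to score = 90 + onset day − visit day, for a stroke with onset on or before the visit.

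- Smallest gap: onset day 0, visit day 37: 90 + 0 − 37 = 53 days.
- Largest gap: onset on the day of the visit: 90 days.

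The gap is always positive, so no stroke captured in this cohort reaches its 90-day score before the subject leaves.

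**2. Which class is out of reach?**

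Disabling requires both an mRS of at least 2 at 90 days and a rise of at least one category. The first condition cannot be observed, so the class cannot be confirmed. Non-disabling can be reached by its second branch (no rise), which has no stated time. That needs a pre-stroke mRS, and neither Table 11.1-1 nor the baseline list in Section 11.4 names one, although Section 11.4 leaves the specific data points to the eCRFs. Deaths and stroke-free subjects can be scored as planned.

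**3. Size**

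Weight of one subject: 1/80 = 1.25 percentage points.

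The documents give no stroke rate. I assume a 30-day non-fatal stroke rate p of 1%, 3% or 5%. Expected strokes = 80p. Chance of at least one = 1 − (1 − p)^80. For mortality m, the composite is m if unconfirmed strokes are not counted and m + p if all are. I take m = 10% (the protocol's expected rate, Section 12.1.1.2, set for the main cohort) and m = 1.7% (1/60, REPRISE II, Section 4.2.1.2).

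| Assumed p | Expected strokes in 80 | Chance of at least one | m = 10%: none / all counted | m = 1.7%: none / all counted |
|---|---|---|---|---|
| 1% | 0.8 | 55% | 10% / 11% | 1.7% / 2.7% |
| 3% | 2.4 | 91% | 10% / 13% | 1.7% / 4.7% |
| 5% | 4.0 | 98% | 10% / 15% | 1.7% / 6.7% |

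These are outer limits, because any stroke validly classed as non-disabling narrows the range.

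**4. Against sampling error**

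The exact 95% interval for 8 events in 80 is 4.4% to 18.8%, and for 1 in 80 it is 0.03% to 6.8%. Each contains the corresponding range in the table.

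**The case against.** Several points on the other side have force.

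- **It is a conflict, not pure silence.** Note 5 asks for a 90-day mRS after any stroke, in every cohort. Table 21.3-1 asks for all new and updated information on serious VARC events through the end of the study, which might allow a later update. This stands as a description of the problem, but it does not remove it: Section 11.9 and footnotes 9 and 10 of Table 11.1-1 end participation and event collection at 30 days, and no visit in this cohort supports the later score.
- **Strokes are not all unclassifiable.** A reader might infer that no non-fatal stroke can be classed at all. The untimed second branch of the non-disabling definition does not support that. The narrower statement, that none can be confirmed as disabling, does hold.
- **A rule may exist elsewhere.** Section 22.2 places adjudication procedures in the CEC charter, which is not supplied; nor are the eCRFs. It would go too far to say that no rule exists. The supplied documents contain none.
- **The consequence is small.** The cohort is meant to assess implantation technique, the endpoint is descriptive, and the range is within sampling error. This stands and limits the weight of the point. Sampling error is nevertheless no reason to leave the definition of the reported quantity open.
- **The VARC composite should be kept.** Section 7.2 follows current VARC guidelines, so replacing the composite outright would do more than is needed. This stands, and the fix below adds to the composite instead of replacing it.

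**Conclusion.** The point holds in this form: within additional-cohort participation, the disabling class that the 30-day composite needs can never be met, and the supplied documents do not say how the affected strokes are counted. Read literally, the composite adds nothing to the cohort's primary endpoint.

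Each non-fatal stroke moves the result by up to 1.25 percentage points. Under the assumed stroke rates of 1% to 5%, the total range is 1 to 5 points, and at least one affected subject is more likely than not. The date conflict needs no assumption; the size rests on those assumed rates and on a cohort of 80.

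A reader might carry the point over to the study's main conclusions. The documents do not support that. The additional cohort's primary endpoint is mortality, the powered main-cohort tests concern 30-day mortality and pre-discharge aortic regurgitation, and implanted main-cohort subjects are still in follow-up at 90 days. The correction is worth making, but it concerns one descriptive secondary endpoint.

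**What to change.** 1. Reconcile the stroke definition and Note 5 in Table 26.2-1 with Section 11.9 and Table 11.1-1, so that the protocol says whether, and how, a 90-day mRS is expected in the additional cohort.
2. For that cohort, report death or any stroke at 30 days alongside the death/disabling-stroke composite.
3. Give the number of strokes without a 90-day mRS, and show the composite twice: with these counted as disabling and as non-disabling. If the CEC charter already has a rule, state it in the analysis plan.

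**Cost.** No new data are needed: strokes in this cohort are already collected through 30 days (Section 8; Table 11.1-1, footnote 9) and adjudicated (Section 22.2). The change is to wording, with approvals if Section 14 applies, and the results table becomes slightly longer. The limitation is that death or any stroke gives minor strokes the same weight as disabling ones, which is why it should stand beside the composite and not replace it.
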